### **8.2.5 Direct access to source data / documents**

The investigator / institution will permit trial-related monitoring, audits, IRB / IEC review and regulatory inspection, providing direct access to all related source data / documents. eCRFs and all source documents, including progress notes and copies of laboratory and medical test results must be available at all times for review by the sponsor's clinical trial monitor and inspection by health authorities (e.g. FDA). The Clinical Research Associate (CRA) / on site monitor may review all eCRFs, and written informed consents. The accuracy of the data will be verified by reviewing the documents described in Section 8.2.4.

## **8.3 QUALITY ASSURANCE AUDIT**

A quality assurance audit of this trial may be conducted by the sponsor or sponsor's designees. The quality assurance auditor will have access to all medical records, the investigator's trial-related files and correspondence, and the informed consent documentation that is relevant to this clinical trial.

## **8.4 PROCEDURES**

### **8.4.1 Adverse events**

An adverse event (AE) is defined as any untoward medical occurrence, including an exacerbation of a pre-existing condition, in a patient in a clinical investigation who received a pharmaceutical product. The event does not necessarily have to have a causal relationship with this treatment.

All adverse events occurring during the course of the clinical trial (i.e., from signing the informed consent onwards through the observational phase) will be collected, documented and reported to the sponsor by the investigator according to the specific definitions and instructions detailed in the 'Adverse Event Reporting' section of the Investigator Site File.

A serious adverse event (SAE) is defined as any AE which results in death, is immediately life-threatening, results in persistent or significant disability / incapacity, requires or prolongs patient hospitalisation, is a congenital anomaly / birth defect, or is to be deemed serious for any other reason representing a significant hazard, which is comparable to the aforementioned criteria.

All adverse events, serious and non-serious, will be fully documented on the appropriate CRF(s) / eCRFs. For each adverse event, the investigator will provide the onset, end, intensity, treatment required, outcome, seriousness and action taken with the investigational drug. The

investigator will determine the relationship of the investigational drug to all AE as defined in the 'Adverse Event Reporting' Section of the Investigator Site File.

The basis for judging the intensity of the AE as well as the causal relationship between the investigational product and the AE is described below.

#### Intensity of event

According to CTCAE criteria version 3.0 (see ISF)

#### Causal relationship

Medical judgment should be used to determine the relationship, considering all relevant factors, including pattern of reaction, temporal relationship, de-challenge or re-challenge, confounding factors such as concomitant medication, concomitant diseases and relevant history. Assessment of causal relationship should be recorded in the case report forms. <For Japan> *The reason for the decision on causal relationship needs to be provided in the CRF.*

- Yes: There is a reasonable causal relationship between the investigational drug administered and the AE.
- No: There is no reasonable causal relationship between the investigational drug administered and the AE.

If a SAE is reported from a still blinded trial, the causal relationship must be provided by the investigator for all potential trial drugs, i.e. the BI trial drug and for all other trial drugs (i.e. any active comparator or placebo according to the trial design).

The investigator has the obligation to report AEs during the specified observational phase. If defined in the CTP, the investigator also has the responsibility to report AEs occurring in a certain period after a patient completes the trial. Any AEs reported to the sponsor during this phase must be documented in the safety database.

If not stipulated differently in the ISF, SAEs are to be reported to the sponsor using the BI Serious Adverse Event Report Form including a documented causal relationship assessment and providing as much detail regarding the SAE as possible. With receipt of follow-up information, all remaining fields on the SAE form are to be completed or updated.

Any serious or significant AE, whether or not considered related to the investigational product, and whether or not the investigational product has been administered, must be reported immediately by telephone / fax to the sponsor. Expedited reporting of serious adverse events, e.g. suspected unexpected serious adverse reactions (SUSARs), will be done according to local regulatory requirements. Further details regarding this reporting procedure are provided in the ISF.

Following every such telephone / fax reports, the Clinical Monitor must provide a written report of the serious or significant AE and any sequelae to Corporate Drug Safety according to the appropriate Corporate SOP(s). These narratives, which confirm the information collected by telephone, may give additional information not available at the time of the initial report.

#### **8.4.2 Emergency procedures**

Not applicable.

### **8.5 RULES FOR AMENDING PROTOCOL**

All CTP amendments must be documented, dated and signed by all signatories (or their successors) of the original protocol. This also applies to any local amendment that may become necessary. Amendments need to be submitted to the IEC for review/approval and to the competent authority (CA) for approval.

### **8.6 DISCONTINUATION OF THE TRIAL BY THE SPONSOR**

Boehringer Ingelheim reserves the right to discontinue the trial at any time for the following reasons:

- 1.) Failure to meet expected enrolment goals,
- 2.) emergence of any efficacy/safety information that could significantly affect continuation of the trial *<if applicable>, or any other administrative reasons, i.e. <add pre-specified reasons>*,
- 3.) violation of GCP, the CTP, or the contract by a trial site or investigator, disturbing the appropriate conduct of the trial.

The investigator / the trial site will be reimbursed for reasonable expenses incurred in case of trial termination (except in case of the third reason).

### **8.7 STATEMENT OF CONFIDENTIALITY**

Individual patient medical information obtained as a result of this trial is considered confidential and disclosure to third parties is prohibited with the exceptions noted below. Patient confidentiality will be ensured by using patient identification code numbers.

Treatment data may be given to the patient's personal physician or to other appropriate medical personnel responsible for the patient's welfare. Data generated as a result of the trial need to be available for inspection on request by the participating physicians, the sponsor's representatives, by the IEC and the regulatory authorities, i.e. the CA.

### **8.8 PUBLICATION POLICY**

Boehringer Ingelheim is as much as possible dedicated to support process of free exchange of relevant scientific information. Any publication of the result of this trial must be consistent with the Boehringer Ingelheim publication policy. The rights of the investigator and of the sponsor with regard to publication of the results of this trial are described in the investigator contract. As a general rule, no trial results should be published prior to finalization of the Clinical Trial Report (CTR).

## **8.9 COMPLETION OF TRIAL**

The EC/competent authority in each participating EU member state needs to be notified about the end of the trial (last patient/patient out, unless specified differently in Section 6.2.3 of the CTP) or early termination of the trial.

## 10. APPENDICES

### 10.1 HANDLING OF PLASMA AND URINE DATA AND DERIVATION OF PHARMACOKINETICS PARAMETERS

Analyte plasma concentrations will be plotted graphically versus time for all subjects as listed in the analyte plasma concentration-time tables. For the presentation of the mean profiles, the arithmetic/geometric mean and the planned blood sampling times will be used.

Concentrations will be used for calculations in the format that is reported in the bioanalytical report. The data format for descriptive statistics of concentrations will be identical with the data format of the respective concentrations. For the calculation of pharmacokinetic parameters, only concentrations within the validated concentration range will be used. The descriptive statistics of pharmacokinetic parameters will be calculated using the individual values with the number of decimal places as provided by the evaluation program. Then the individual values as well as the descriptive statistics will be reported with three significant digits in the clinical trial report. The actual sampling times will be used. For predose samples, the actual sampling time will be set to zero.

Concentration data identified with NOS (no sample available), NOR (no valid result), NOA (not analyzed), BLQ (below the limit of quantification), and NOP (no peak detectable) will be ignored and not replaced by zero at any time point (applies also to the lag phase including the pre-dose value). Descriptive statistics of concentrations at specific time points will be calculated only when at least 2/3 of the individuals have concentrations within the validated concentration range. The overall sample size to decide whether the “2/3 rule” is fulfilled will be based on the total number of samples intended to be drawn for that time point (i.e., BLQ, NOR, NOS, NOA, NOP are included).

Non-compartmental pharmacokinetic parameters will be determined using WinNonlin or another validated program.

In the non-compartmental analysis, concentration data identified with NOS, NOR, and NOA will not be considered. BLQ and NOP values in the lag phase will be set to zero. The lag phase is defined as the period between time zero and the first time point with a concentration above the quantification limit. All other BLQ and/or NOP values of the profile will be ignored.

If the predose concentration before the first dose is less than or equal to 5% of Cmax value in that subject, the subject's data without any adjustments can be included in all pharmacokinetic measurements and calculations (i.e., the predose value will not be changed to zero). If the predose value is greater than 5% of Cmax, the subject should be dropped from all statistical evaluations. The individual pharmacokinetic parameters can be calculated and listed separately.

Every effort will be made to include all concentration data in an analysis. If not possible, a case to case-to-case decision is required whether the value should only be excluded from half-life estimation or the complete analysis.

- If a concentration is only excluded from half-life determination, it will be used for all other calculations (e.g., descriptive statistics) and for graphical presentation.
- If a concentration value is excluded from all calculations, it will not be presented graphically or used for the calculation of descriptive statistics and parameter determination. . However, the excluded concentration itself will be listed in the clinical trial report associated with an appropriate flag.

Descriptive statistics of parameters are calculated only when at least 2/3 of the individual parameter estimates of a certain parameter are available. . If the actual sampling time will not be recorded or will be missing for a certain time point, the planned time will generally be used for this time point instead. Pharmacokinetic parameters which cannot be determined will be identified by "not calculated" (NC).

**Cmax and tmax:** Individual Cmax and tmax values will be directly determined from the plasma concentration time profiles of each subject. If the same Cmax concentration occurs at different time points, tmax is assigned to the first occurrence of Cmax.

**Estimation of λz:** The apparent terminal rate constant λz will be estimated from a regression of ln(C) versus time over the terminal log-linear disposition portion of the concentration-time profiles. The log-linear profiles, which include the regression line through the terminal points, will be checked via visual inspection, and it will be determined whether the regression appropriately represents the terminal slope. A minimum of three points will be used in the determination of λz. If the last concentration-time point increases, this time point may be included if the t1/2 estimate is reasonable. If λz is not determinable then consequently only parameters not requiring λz will be reported. In addition, the lower (tλz,start) and upper (tλz,end) limit on time for values to be included in the calculation of λz will be listed.

**t1/2:** The terminal half-life will be calculated from the terminal rate constant using the equation

$$t_{1/2} = \frac{\ln 2}{\lambda_z}$$

**AUC:** The area under the curve will be calculated using the linear up/log down algorithm. If an analyte concentration is equal to or higher than the preceding concentration, the linear trapezoidal method will be used. If the analyte concentration is smaller than the preceding concentration, the logarithmic method will be used.

*Linear trapezoidal rule (t2 > t1 and Ct2 ≥ Ct1):*

The area of the trapezoid between the two data points ( $t_1, C_{t1}$ ) and ( $t_2, C_{t2}$ ) will be computed by:

$$AUC_{t1-t2} = 0.5 \times (t_2 - t_1) \times (C_{t1} + C_{t2})$$

*Logarithmic trapezoid rule ( $t_2 > t_1$  and  $C_{t2} < C_{t1}$ ):*

The area of the trapezoid between the two data points ( $t_1, C_{t1}$ ) and ( $t_2, C_{t2}$ ) will be computed by:

$$AUC_{t1-t2} = \frac{(t_2 - t_1) \times (C_{t2} - C_{t1})}{\ln(C_{t2}/C_{t1})}$$

**AUC0-∞:** The area under the plasma concentration-time curve over the time interval from 0 extrapolated to infinity will be calculated according to the following equation

$$AUC_{0-\infty} = AUC_{0-tz} + \frac{C'_{tz}}{\lambda_z}$$

where  $C'_{tz}$  is the concentration predicted by the regression line for the time  $t_z$  (time of last measurable concentration of the analyte in plasma). The area under the concentration-time curve over the time interval from 0 to the last quantifiable plasma concentration ( $AUC_{0-tz}$ ) will be calculated by the linear up/log down method as described above.

**%AUCtz-∞:** The percentage of the  $AUC_{0-\infty}$  will be obtained by extrapolation according to the following equation:

$$\% AUC_{tz-\infty} = \frac{AUC_{0-\infty} - AUC_{0-tz}}{AUC_{0-\infty}} \times 100$$

**MRT:** The mean residence time after intravenous bolus injection will be calculated as follows:

$$MRT = \frac{AUMC_{0-\infty}}{AUC_{0-\infty}}$$

In order to compare the mean residence time after intravenous bolus administration (MRT) and intravenous infusion (MRTinf), the following equation will be used in addition, where T represents the infusion time.

$$MRT = MRT_{inf} - (T \times 0.5)$$

The area under the first moment curve from time 0 to infinity (AUMC0-∞) is calculated according to:

$$AUMC_{0-\infty} = AUMC_{0-tz} + \frac{C'_{tz} \times tz}{\lambda_z} + \frac{C'_{tz}}{\lambda_z^2}$$

**CL:** The total clearance after intravenous administration will be determined according to the following equation:

$$CL = \frac{\text{Dose}}{AUC_{0-\infty}}$$

(F = absolute bioavailability factor)

**Vz:** The apparent volume of distribution during the terminal phase after intravascular administration will be determined according to the following equation:

$$V_z = \frac{CL}{\lambda_z}$$

**Vss:** After single intravenous bolus administration or intravenous infusion when the mean residence time has been adapted as described above, the distribution volume in the steady state will be calculated according:

$$V_{ss} = CL_{ss} \times MRT_{ss}$$

**fet1-t2:** The fraction excreted is calculated according to

$$fe_{t1-t2} = \frac{Ae_{t1-t2}}{\text{Dose}} \times 100$$

where **Aet1-t2** is the total quantity of the analyte that is excreted in urine over the time interval t1 to t2. This may represent the product of urine volume and urine analyte concentration for one time interval, as well as the cumulative amounts excreted calculated as the sum of the excreted amounts of subsequent time intervals.

**CLR,t1-t2:** The renal clearance (CLR) will be calculated as the quotient of the quantity of the analyte that is excreted in urine from the time point t1 until the time point t2 (Aet1-t2) and the area under the concentration-time curve within the same time interval (AUCt1-t2).

$$CL_{R,t1-t2} = \frac{Ae_{t1-t2}}{AUC_{t1-t2}}$$

**gMean, gCV:** The geometric mean (gMean) and coefficient of variation, gCV (given in %), will be calculated by the formulae:

$$gMean = \exp \left[ \frac{1}{n} \sum_{i=1}^n \ln(x_i) \right] = \exp \left[ \ln(\bar{x}) \right]$$

$$gCV(\%) = 100 \cdot \sqrt{\exp [Var(\ln(x_i))] - 1}$$

where

$$Var(\ln(x_i)) = \frac{1}{n-1} \sum_{i=1}^n \left[ \ln(x_i) - \bar{\ln(x_i)} \right]^2.$$

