### 7.3.2 Secondary analyses

The secondary analysis will evaluate safety, pharmacokinetics and tumour response.

- Pharmacokinetic analyses

All evaluable subjects will be included in the pharmacokinetic analysis. Subjects who are considered as not evaluable will be listed with their individual plasma concentrations and individual pharmacokinetic parameters, however, will not be included in descriptive statistics for plasma concentrations, pharmacokinetic parameters or other statistical assessment.

A subject is considered to be not evaluable if the subject has an important protocol violation relevant to the evaluation of pharmacokinetics or has insufficient data.

The following descriptive statistics will be calculated for analyte concentrations as well as for all pharmacokinetic parameters: N, arithmetic mean, standard deviation, minimum, median, maximum, arithmetic coefficient of variation, geometric mean, geometric coefficient of variation (refer also to 10.1).

Refer to Appendix 10.1 for details concerning handling and derivation of pharmacokinetic parameters.

If sufficient patients are entered into the study, covariates such as gender, age, and weight may be exploratively investigated for their potential influence on pharmacokinetic parameters. Exploratory analyses will compare the area under the plasma concentration-time profile and the maximum plasma concentration with considered relevant safety, efficacy, and pharmacodynamic endpoints.

- Efficacy analyses

Tumour response, objective response (CR, PR), and best overall response will be analysed descriptively according to the RECIST criteria (see section 5.1.2 and Appendix 10.4) at the end of every other treatment course.

For patients with no measurable lesion the overall response will be assessed as NEV (compare Table 10.4.4: 2). If data allow the assessment of the non-target lesion will be described in a explorative subgroup analysis.

The time to tumour progression will be defined as the time from first treatment administration to cancer progression or death due to the cancer under study.

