### 7.3.4 Interim analyses

A pharmacokinetic interim analysis will be performed as soon as pharmacokinetic data of a sufficient number of patients are available and clean. A repeat pharmacokinetic interim analysis will be performed if requested. In contrast to the final pharmacokinetic calculations, the interim analysis will be based on planned sampling times rather than on actual times. Therefore, minor deviations of interim and final results may occur. The interim analysis will provide mean concentration-time profiles and summary statistics of pharmacokinetic

parameters/individual values without trial subject identification. The interim results will be distributed to the Investigator/trial team

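### Where some, but at most a third, of plasma concentrations at a time point are below the quantification limit, Appendix 10.1 drops them as if missing, so the reported concentration summaries describe only the quantifiable patients and are biased upward

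*Protocol*

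**What the plan says.** Protocol Appendix 10.1 defines five flags for a concentration without a usable value: no sample (NOS), no valid result (NOR), not analysed (NOA), below the limit of quantification (BLQ) and no peak detectable (NOP). For the concentration statistics all five are handled alike: they "will be ignored and not replaced by zero at any time point (applies also to the lag phase including the pre-dose value").

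A reporting threshold follows. Statistics at a time point "will be calculated only when at least 2/3 of the individuals have concentrations within the validated concentration range". The denominator "will be based on the total number of samples intended to be drawn for that time point", so BLQ and missing samples both count against it.

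These statistics are used in three places:

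- Section 7.3.2 makes them a planned output: "The following descriptive statistics will be calculated for analyte concentrations as well as for all pharmacokinetic parameters". The list includes N, arithmetic and geometric mean, median, minimum, and arithmetic and geometric CV.
- Appendix 10.1 builds the mean profiles on them: "For the presentation of the mean profiles, the arithmetic/geometric mean and the planned blood sampling times will be used".
- Section 7.3.4 sends such profiles to the investigator and trial team at the interim: "The interim analysis will provide mean concentration-time profiles and summary statistics of pharmacokinetic" parameters or individual values.

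The non-compartmental analysis has a separate rule in the same appendix. There NOS, NOR and NOA are left out, BLQ and NOP in the lag phase are set to zero, and later BLQ and NOP values are skipped within the patient's own profile.

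**The concern.** NOS, NOR and NOA carry no information about the concentration. BLQ and NOP do: they say that it was low. Leaving them out of a summary selects patients on the value being summarised, and always from the bottom. Location statistics can then only move up, and the spread shrinks. The non-compartmental rule shows that the protocol knows the difference between the two groups. The concentration tables do not use it.

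What is at stake is how the concentration tables and mean profiles are read. They appear to describe a dose cohort, but at an affected time point they describe only its quantifiable members. Cohorts are small (3 to 6 patients, 24 at the MTD), so one dropped patient is a large share. Doses start at 12 mg and reach at least the 300 mg named in SAP section 3.2, and sampling runs to 336 h. If BLQ results occur, low doses and late times are the natural place for them, so the bias could differ between the curves a reader compares. The median, normally the safe fallback, is computed after the same deletion.

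**Working it through.** The plan states no figure on this point, so there is none to reproduce.

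**Inputs from the documents.** The deletion rule and the two-thirds threshold (Appendix 10.1); cohort sizes 3, 6 and 24 (Synopsis).

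**Inputs assumed.** Log-normal concentrations with geometric CV (gCV) of 30%, 50% or 80%, and BLQ shares up to the maximum the rule allows. The documents give neither the quantification limit nor the variability.

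**Step 1: how many can be dropped.** With two thirds of intended samples required, a statistic is still reported with 1 of 3, 2 of 6 or 8 of 24 values BLQ, and with fewer if samples are also missing.

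**Step 2: bound without a distribution.** Let m of n analysed values be kept. Concentrations are non-negative, so reported mean / full mean ≤ n/m ≤ 1/(2/3) = 1.5. The arithmetic mean is never more than 1.5 times the cohort's own full mean.

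**Step 3: size for a large group.** With σ = √ln(1 + gCV²), dropping the lowest fraction f multiplies the geometric mean by exp[σ·φ(z_f)/(1 − f)]. For f = 1/3, φ(z_f)/(1 − f) = 0.545; for f = 0.2 it is 0.350.

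| gCV | σ | f = 0.2 | f = 1/3 |
|---|---|---|---|
| 30% | 0.294 | 1.108 | 1.174 |
| 50% | 0.472 | 1.180 | 1.294 |
| 80% | 0.703 | 1.279 | 1.468 |

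**Step 4: size at the trial's cohort sizes, gCV 50%.** The factor is exp(σ·k̄), where k̄ is the average expected standard normal order statistic of the values kept. The expected lowest of 3 is −0.846; the two lowest of 6 are −1.267 and −0.642.

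- 1 of 3 BLQ: k̄ = 0.846/2 = 0.423; exp(0.472 × 0.423) = 1.22
- 1 of 6 BLQ: k̄ = 1.267/5 = 0.253; exp(0.472 × 0.253) = 1.13
- 2 of 6 BLQ: k̄ = (1.267 + 0.642)/4 = 0.477; exp(0.472 × 0.477) = 1.25
- 8 of 24 BLQ, by simulation: 1.28

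**Step 5: median and spread, gCV 50%, one third BLQ, large group.** The median of the kept values is the two-thirds quantile of all values: exp(0.472 × 0.431) = 1.23. The log-scale SD falls to 0.684 of its true value: 0.684 × 0.472 = 0.323, and √[exp(0.323²) − 1] = 0.33. A true gCV of 50% is reported as 33%.

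**Step 6: the rule applied with a fixed limit.** Simulating cohorts of 3, 6 and 24 with true BLQ shares of 10%, 20% and 33% and gCV of 30% to 80%, among reported cohorts with at least one BLQ value, gave reported/full-cohort ratios of 1.05 to 1.35 for the arithmetic mean and 1.06 to 1.58 for the geometric mean. With no BLQ value the ratio is 1.

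**Step 7: is a BLQ-ranked median always known?** With N intended samples, m ≥ 2N/3 are quantifiable and BLQ values b ≤ N − m ≤ N/3. Hence b/(m + b) ≤ 1/3 even if other samples are missing. The middle rank or ranks are therefore quantifiable, and the median of all analysed samples needs no imputation.

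**The case against.** The strongest reply is that this is a limitation of a descriptive display that may never arise. Several parts of it stand.

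- **Occurrence is unknown.** A reader might infer that the late or low-dose mean profiles are in fact biased. The documents give no quantification limit, half-life or expected concentrations; if the 168 h and 336 h samples are quantifiable, there is no bias.
- **Most of the cohort is kept.** A reader might also infer that the means describe only the highest patients. They do not: at least two thirds of the intended samples must be quantifiable, and beyond that point no statistic is shown.
- **The stated endpoints do not use these statistics.** It would be tempting to carry the bias over to half-life, AUC or dose proportionality. Section 2.3 names pharmacokinetic parameters as the endpoint. Appendix 10.1 derives these patient by patient under a separate BLQ rule, with the terminal slope from individual profiles. Section 7.1.2 explores dose proportionality on Cmax and AUC, and the MTD rests on DLT.
- **Some transparency exists.** "Analyte plasma concentrations will be plotted graphically versus time for all subjects", and N is reported. A reduced N shows that values were lost, but not whether they were low or missing.
- **The operative rule may be elsewhere.** SAP sections 6.6 and 7.5 send pharmacokinetic missing data and concentration summaries to sources that are blacked out. They may add detail, but cannot be assumed to override a clear rule in the protocol.

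Replacing BLQ by zero would be no cure: it biases the arithmetic mean downward and leaves the geometric mean undefined. These points limit the scope and weight of the concern. They do not justify treating a known low value as missing.

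**Conclusion.** The point holds as a conditional one. Whenever a time point has at least one BLQ or NOP value and still meets the two-thirds rule, the mean, geometric mean and median are overstated for the cohort, the minimum is too high and the CV too low. The direction follows from the rule itself; the size depends on assumptions. With log-normal concentrations and gCV 50%, the geometric mean is overstated by about 13% (1 of 6), 22% (1 of 3) or 25% (2 of 6). With one third BLQ in a large group, it is 17% at gCV 30% and 47% at gCV 80%. Whether any time point is affected cannot be told from the documents.

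The consequence is confined to the concentration tables and mean profiles, including those circulated at the interim. Nothing here supports the conclusion that a parameter, the dose-proportionality exploration or the MTD is wrong. The change is worth making because it is nearly free.

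**What to change.** In Appendix 10.1, for the concentration tables and profiles only:

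1. Keep NOS, NOR and NOA as missing. After the first quantifiable sample, rank BLQ and NOP results below every quantifiable value.
2. At each reported time point give the number BLQ or NOP, the median over all analysed samples with those results ranked lowest, and the minimum as <LLOQ where one occurs.
3. Keep the arithmetic and geometric means and the CVs, but flag them as based on quantifiable samples only wherever a BLQ or NOP value occurs.
4. Plot the BLQ-ranked median profile next to the mean profile at all reported times, at the interim as well.

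Leave the two-thirds rule and the non-compartmental rules unchanged.

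Three stronger remedies are not recommended. Suppressing the mean after any BLQ value would remove it from a 24-patient cohort to avoid a bias of about 4% (1 of 24, gCV 50%). Switching from arithmetic mean to median partway along a curve would create an artificial drop: the ratio of mean to median is √(1 + CV²), which is 1.12 at 50% and 1.28 at 80%, a fall of 11% to 22%. A censored log-normal fit with 1 of 3 BLQ would estimate two parameters from two observed values.

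The cost is wording in Appendix 10.1 and the table programs, one extra row or footnote per table, and one extra profile per dose. No new data are needed.
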